- $^{\fbox{2}}$ Evaluate the factors associated with an incomplete extirpation in each group.
- ² Evaluate the factors associated with a failed cold polypectomy.

4. Design

Randomized clinical trial comparing two endoscopic techniques.

5. Methods

Population to study

The study population includes patients scheduled to perform a colonoscopy in a non-urgent way. The patient will be invited to participate before performing the colonoscopy.

The variables defined in Annex 1 will be collected in a dissociated form database.

Inclusion and exclusion criteria

The inclusion criteria are:

• Patients older than 18 years scheduled to undergo a colonoscopy.

The exclusion criteria are:

- Absence of lesions of 5-9 mm.
- Contraindication for polypectomy (anticoagulant treatment, treatment with clopidogrel, coagulopathy or severe thrombocytopenia)
- Loss of polypectomy specimen
- Refusal to participate

Randomization

It will be done once the patient agrees to participate in the work and the first candidate polyp has been identified. Each patient will be randomized (regardless of the number of injuries per patient) in such a way that all lesions of each patient will be removed in the same way. It will be stratified by endoscopist, in such a way that each endoscopist will have its sequence of sealed randomization. Within each stratum a pure randomization will be carried out through a sequence generated by computer where the probability of belonging to each group will be 0.5. A total of 60 numbered sealed opaque envelopes will be available for each endoscopist that will be stored in the endoscopy room and will be opened consecutively as patients are included.

Intervention

Patients who meet the inclusion criteria and do not present any exclusion criteria (preendoscopic) will be invited to participate in the study. The informed consent will be completed according to the law 41/2002 of autonomy of the patient without it being altered the relationship with your doctor or any damage to your treatment.

1) Endoscopic act

The interventions will be carried out in each of the participating centers. The scans will be performed under sedation according to the protocols established in each center. Once the lesion is identified, the method of extirpation of the lesion will be randomized.

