Assuming a proportion of incomplete polypectomies in both groups of 10% (using the taking of biopsies as a diagonostic pattern) and setting an equivalence limit of 7%, a total of 315 lesions per group are estimated to have an α risk of 5% and a power of 80%. Assuming a proportion of losses (polyps not recovered for histological study, polypectomies of the failed Cold group of 20%), an estimated 394 lesions per group are needed, with a total of 788 lesions in total.

Data Collect

All the variables concerning the characteristics of the endoscopist, the patient and the injuries included will be collected in each center. The variables related to the histological diagnosis will be collected in the same way in the respective center. The variables concerning the follow-up will be collected in a centralized manner, through a telephone call that will be made between 3 and 4 weeks from the procedure. The variable related to the histological study of the base of the polyp will be collected in a centralized manner by the pathologist in charge of the analysis of the samples.

6. Data management

Data from the data collection notebooks will be merged by the main researcher or collaborating researchers anonymously, encrypted and dissociated from the clinical information by means of a patient identification code (ID), in a database made through the program Access (Microsoft Corporation, Redmond, WA USA). A copy of the database will be used in each participating center, which will be merged after completing the data collection. The responsible researcher will define an ID for each participant. The data entered in the

database will be anonymous and the database will be protected with a password to which only the researchers will have access.

The unified file will be kept at the Río Hortega University Hospital and will be maintained until the end of the study. Regarding the application of the Organic Law on Data Protection 15/1999 and Royal Decree 1720/2007 that develops it, it should be noted that the protocol defined in the project oriented to epidemiological analysis, determines that the files will record information completely anonymized

7. Statistical analysis

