The Access program (Microsoft Corporation, Redmond, WA USA) will be used for the realization of the database and the statistical analysis of them will be carried out through the STATA program (StataCorp, 2013. Stata Statistical Software: Release 13. College Station, TX: StataCorp LP). In the quantitative variables, the arithmetic mean and the standard deviation will be calculated (variables that do not follow a normal distribution according to the Kolmogorov-Smirnov test will be described with median, minimum, maximum and interquartile range), and the qualitative ones will be expressed as percentages and your 95% confidence intervals.

The analysis of the primary objective, the proportion of incomplete polypectomies in both groups will be compared by means of the z test of homogeneity without using the correction of Yates. The confidence interval of the difference between the two groups will also be estimated. The analysis will be carried out by intention to treat, regardless of the type of polypectomy performed and per protocol (assigning the lesions assigned to the group Cold that are extirpated with hot snare to the Hot group). To evaluate possible confounding factors (endoscopist, nurse, handle type, location ...), the STATA confound user command will be used, defining as a significant change that which conditions a change in the odds ratio greater than 10% with respect to the one obtained with the complete model. In case several models do not present differences greater than 10%, the most parsimonious will be chosen.

Within the secondary objectives, the proportion of complications in both groups will be verified by the de2 test. To evaluate the factors associated with incomplete polypectomies and those associated with failed cold polypectomy, multivariate logistic regression techniques will be used.

8. Ethical aspects

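### The supporting adjusted analysis of the primary endpoint is chosen from the outcome data by a 10% change-in-odds-ratio screen, and is not on the scale of the 7-point limit

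*Combined protocol and SAP*

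**What the plan says.** Section 7 (Statistical analysis) compares the primary endpoint by a z test without Yates correction and gives an interval for the difference between the groups. It does so by intention to treat and in a per-protocol analysis that moves Cold lesions removed with a hot snare into the Hot group. The Abstract names the same test and interval for the primary objective and no adjusted analysis.

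The same paragraph of section 7 then turns to confounding. The candidates are endoscopist, nurse, handle type and location, and the list ends in dots. The screen works by "defining as a significant change that which conditions a change in the odds ratio greater than 10" per cent relative to the complete model. "In case several models do not present differences greater than 10%, the most parsimonious will be chosen".

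The only decision limit is in section 5, Sample size: "setting an equivalence limit of 7" per cent. Under Randomization in section 5, patients are allocated by simple randomisation within endoscopist, where "the probability of belonging to each group will be 0.5", and all lesions of one patient are removed by the same technique.

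**The concern.** A change in the odds ratio can be computed only from allocation and outcome together, so the covariates of the adjusted analysis are settled after the outcome is known. Because the candidate list is open, the complete model that serves as the reference is not settled in advance either.

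By intention to treat, the screen has no systematic confounding to find: factors fixed before allocation differ between arms by chance. The odds ratio is also non-collapsible, so it can shift when a prognostic covariate is added even if the arms are perfectly balanced. Endoscopist, the stratification factor, is only one candidate and may be dropped.

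The product is an odds ratio, whereas the trial is sized on a difference in proportions, and the plan gives neither an odds-ratio limit nor a conversion. If adjusted and unadjusted results diverged, a reader could not tell signal from selection, nor place the adjusted result against the limit.

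**Working it through.** **Scale of the limit.** The inputs, from section 5, Sample size, are "Assuming a proportion of incomplete polypectomies in both groups of 10" per cent, a 7% limit whose scale is not named, and "a total of 315 lesions per group are estimated to have an α risk of 5% and a power of 80" per cent. Two one-sided tests at 5% each, with the 20% type II error split as 10% per side, give

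n = 2 × 0.10 × 0.90 × (1.645 + 1.282)² / 0.07² = 0.18 × 8.567 / 0.0049 = 314.7, so 315 per group.

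With 20% losses, 315 / 0.80 = 393.75, so 394 per group and 788 in total, as stated: "an estimated 394 lesions per group are needed, with a total of 788 lesions in total". The alternatives tried do not give 315: two one-sided tests at 2.5%, 386; non-inferiority at one-sided 5% or 2.5%, 228 or 289; superiority of 10% v 17%, 373; superiority of 10% v 3%, 194. The limit is therefore an absolute difference of 7 points.

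**The limit as an odds ratio.** OR = [p₁/(1 − p₁)] / [p₀/(1 − p₀)] with p₁ = p₀ + 0.07:

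| Reference rate | OR for +7 points |
|---|---|
| 6.8% | 2.19 |
| 10% | (0.17/0.83)/(0.10/0.90) = 1.84 |
| 20% | (0.27/0.73)/(0.20/0.80) = 1.48 |
| 30% | 1.37 |

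The OR for −7 points is 0.28 at 10% and does not exist at 7% or below. In the other direction, an OR of 1.84 is +5.1 points at 6.8%, +7.0 at 10% and +11.5 at 20%. The Introduction cites 6.8% from biopsy-based studies and close to 30% from a margin-based one; 20% is illustrative. No single odds ratio stands for 7 points unless the reference rate is fixed.

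**Size of the trigger relative to noise.** Expected events are 630 × 0.10 = 63. SE(log OR) = √[2 × (1/31.5 + 1/283.5)] = 0.266. The trigger is ln(1.1)/0.266 = 0.0953/0.266 = 0.36 standard errors. At a 10% rate, an OR of 1.1 gives odds of 0.1222, a risk of 10.89% and hence +0.89 points.

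**How often the rule keeps covariates with nothing to adjust for.** The documents do not give the numbers of endoscopists, nurses, handle types or locations, so all are assumed. As a bound on endoscopists, 60 envelopes each and 788 lesions need 788/60 = 13.1, so at least 14, at one lesion per patient, or 788/120 = 6.6, so at least 7, at two.

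Simulation A: 630 independent lesions, 10% events, no technique effect, covariates independent of arm, equal numbers of endoscopists and nurses, 3 handle types, 4 locations, 400 trials per cell. The smallest model within 10% of the complete-model OR was kept; between models of equal size, where the plan gives no rule, the closest was taken. Share of trials keeping at least one covariate:

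| Covariate effects (SD, log-odds) | 5 endoscopists | 10 | 15 |
|---|---|---|---|
| 0 | 2% | 8% | 17% |
| 0.3 | 9% | 20% | 26% |
| 0.6 | 28% | 40% | 47% |

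Between 5 and 16 different models were chosen per cell. The ratio of largest to smallest OR over the 16 candidate models had a median of 1.06 to 1.20 and a 90th percentile of 1.10 to 1.36. The Monte Carlo standard error at 47% is √(0.47 × 0.53/400) = 2.5 points.

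Simulation B: 300 trials per setting, with lesion size in place of handle type. A covariate was kept in 15% to 21% of trials with 11 endoscopists, 11 to 20 nurses and 6 locations; in 28% when endoscopists varied (SD 0.4); and in 5% with 6 endoscopists, 6 nurses and 4 locations. Type I error stayed near 5% (Monte Carlo standard error √(0.05 × 0.95/300) = 1.3 points). The complete model raised the SD of the log OR from about 0.28 to 0.30. With 11 endoscopists it has 1 + 10 + (10 to 19) + 5 + 1 = 27 to 36 terms besides the intercept, or 63/36 = 1.8 to 63/27 = 2.3 events per term.

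**The case against.** The strongest reply is that nothing decisive depends on this step. The primary comparison is the unadjusted test and interval, and that interval is already on the scale of the 7-point limit. The plan never says that the adjusted odds ratio will be judged against 7 points. The rule also limits its own damage: a retained model must lie within 10% of the complete model, about 0.9 points at a 10% rate or one eighth of the limit. Most simulated trials kept no covariate, and the frequencies rest on invented counts. Finally, the confounder step follows directly on the per-protocol definition. Moving Cold lesions to Hot makes that an as-treated comparison in which difficult lesions can migrate, so a search for confounding has a real purpose there.

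Most of this stands, and it sets the weight of the point. Two parts do not rescue the rule. Staying close to the complete model is little protection when that model is undefined: stopping the open list at a different place gives a different reference. And possible confounding in the as-treated analysis is a reason to name covariates beforehand, not to let the observed odds ratio choose them.

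**Conclusion.** The point holds for the supporting adjusted analysis only. Its model is selected from outcome data against an undefined reference, and its result has no stated route to the risk-difference scale. With no true confounding, the rule kept a covariate in roughly 2% to 47% of simulated trials. That range depends on assumed numbers of endoscopists, nurses and locations, on assumed covariate effects, and on treating lesions as independent.

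A reader might infer more than the documents support:

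- That the primary result is data-selected. It is not; the test and interval are fixed and unadjusted.
- That the screen inflates false positives. Type I error stayed near 5% where it was checked.
- That every shift in the odds ratio is chance. This is so for imbalance in pre-allocation factors by intention to treat, but not for the as-treated comparison, nor for factors chosen after allocation.
- That an adjusted result can never be set against 7 points. It can, once standardised to a risk difference; the plan simply does not provide for this.

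**What to change.** Delete the change-in-estimate screen from section 7 and specify one supporting adjusted analysis:

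- A logistic model with technique, endoscopist (fixed or random effect, as the stratification factor), lesion size and location. Add morphology only if it is recorded; Annex 1, which lists the variables, was not in the text available for this review.
- Leave out factors that may be chosen after allocation, such as snare (handle) type.
- Standardise the fitted model to a risk difference, with an interval that allows for several lesions per patient.
- Report it beside the unadjusted difference for intention to treat, and use the same fixed covariates for the as-treated analysis that the plan calls per protocol.

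The cost is SAP wording and a little programming; no data beyond the listed covariates are needed and the sample size is unchanged. The drawback is that an imbalance noticed late can enter only as a labelled sensitivity analysis. The gain in precision is small: the variance of the standardised risk difference was 0% to 6% lower than the unadjusted one in simulation, with lesions treated as independent. The reason for the change is one interpretable adjusted answer, not power.

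### The factor models in section 7 make no allowance for lesions sharing an endoscopist, so any endoscopist characteristic entered would be tested with too small a standard error

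*Combined protocol and SAP*

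**What the plan says.** Section 3 lists two factor analyses among the secondary objectives: incomplete removal, examined separately by group, and failed cold polypectomy. Their whole analysis plan is one sentence in section 7: "To evaluate the factors associated with incomplete polypectomies and those associated with failed cold polypectomy, multivariate logistic regression techniques will be used". It gives no candidate factors, unit of analysis, random effect or robust variance.

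Three other statements in section 5 matter:

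- Data Collect: "All the variables concerning the characteristics of the endoscopist, the patient and the injuries included will be collected in each center".
- Randomization: "A total of 60 numbered sealed opaque envelopes will be available for each endoscopist". Patients are randomised within endoscopist, and all lesions of a patient get the same technique.
- Sample size, counted in lesions: "an estimated 394 lesions per group are needed, with a total of 788 lesions in total".

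In the analysis, the endoscopist is named only as a possible confounder, in the paragraph of section 7 on the primary objective. The number of endoscopists is not given. The variable list is in Annex 1, which is not in the text available for this review.

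**The concern.** An endoscopist characteristic, such as experience, has only as many independent values as there are endoscopists. A logistic regression on lesions with no clustering term treats it as having several hundred. If endoscopists differ in their results for reasons outside the model, its standard error is too small and its p-value too low. Failed cold polypectomy is especially exposed, because whether a lesion assigned to the cold snare ends up removed with the hot snare plausibly depends on the operator.

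This is not the same problem as several lesions sharing a patient. Grouping by patient still treats different patients of one endoscopist as independent. Nor does randomisation help, since these factors are not randomised.

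At stake is the reporting of operator characteristics as risk factors by chance. Section 9 also foresees an online calculator or app. It does not say which model would feed it.

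**Working it through.** **1. The plan's own figure.** With p = 0.10 in both groups and margin 0.07, two one-sided 5% tests at 80% power give

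n = 2·p(1−p)·(z0.95 + z0.90)² / 0.07² = 2 × 0.10 × 0.90 × (1.6449 + 1.2816)² / 0.0049 = 314.6, so 315 per group.

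Allowing 20% losses, 315/0.80 = 393.75, so 394. Both figures reproduce. The documents state no error rate for the factor models, so there is nothing further to reproduce.

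**2. How many endoscopists?** With 60 envelopes each, the minimum is 788/(60 × lesions per patient), rounded up. Lesions per patient is an assumption.

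| Lesions per patient | Minimum endoscopists |
|---|---|
| 1 | 14 |
| 1.5 | 9 |
| 2 | 7 |
| 3 | 5 |

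The documents set no maximum. Ten endoscopists would need at least 788/600 = 1.31 lesions per patient.

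**3. Formula.** Take a two-level endoscopist factor with no effect, split evenly over K endoscopists who each contribute m = N/K lesions. Then

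- design effect DE = 1 + (m − 1)·ICC
- actual level of a nominal 5% test = 2·[1 − Φ(1.96/√DE)]
- ICC ≈ p(1−p)·SD², with SD the between-endoscopist standard deviation on the logit scale. At p = 0.10 this is 0.09 × 0.4² = 0.0144 and 0.09 × 0.8² = 0.0576.

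For K = 14:

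| Lesions in the arm | m | DE, SD 0.4 | Level | DE, SD 0.8 | Level |
|---|---|---|---|---|---|
| 394 | 28.1 | 1.39 | 9.7% | 2.56 | 22% |
| 315 | 22.5 | 1.31 | 8.7% | 2.24 | 19% |

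**4. Simulation.** One arm of 394 lesions, 10% events, normal endoscopist intercepts, logistic Wald test at 1.96, 4,000 replicates per cell. Percentage declared significant with no true effect:

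| Endoscopists | SD 0 | SD 0.4 | SD 0.6 | SD 0.8 |
|---|---|---|---|---|
| 10 | 4.4 | 11.2 | 18.7 | 26.7 |
| 16 | 4.7 | 9.1 | 13.5 | 18.9 |
| 24 | 4.9 | 6.7 | 10.6 | 14.5 |

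With 14 endoscopists, a separate simulation gave 9–24% over SD 0.4 to 0.8 at 394 lesions and about 7–16% at 315. A beta-binomial simulation at 315 lesions and 14 endoscopists gave 8%, 10% and 18% at ICC 0.01, 0.02 and 0.05. The methods differ by a few points, which is small beside the uncertainty about SD.

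**5. Does grouping by patient repair it?** With 14 endoscopists and an average of 1.5 lesions per patient, the unadjusted test rejected in 9%, 15% and 23% of runs (SD 0.4, 0.6, 0.8). With patient-clustered standard errors it rejected in 9%, 14% and 22%. It does not.

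**6. Does the remedy work?** A t test on per-endoscopist event counts rejected in 4.3–5.7% of runs. A random-endoscopist-intercept model tested on endoscopist-level degrees of freedom rejected in 3–6%.

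**The case against.** The strongest reply is that the plan is silent here rather than wrong. It names a family of methods, which does not exclude a clustered version. No sentence says that endoscopist characteristics will enter these models, and the absence of Annex 1 from the available text proves nothing. That stands, so the point is conditional. But an analyst who follows the sentence as written has no reason to add a clustering term, and the plan itself collects these characteristics and stratifies by endoscopist.

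Four stronger readings are tempting, and the documents do not support them:

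- **That only a few operators are involved.** The number is not given, and at one lesion per patient at least 14 are needed.
- **That the error applies to all 788 lesions pooled.** The incomplete-removal objective is set by group and the failure objective concerns the cold technique, so per-arm figures are the relevant ones.
- **That the error rate is known to be large.** A wider set of assumptions runs from 7% (30 endoscopists, ICC 0.01) to 48% (6 endoscopists, ICC 0.10). The 10% event rate is the plan's assumption for incomplete polypectomy; no separate rate is given for failed cold polypectomy.
- **That lesion and patient factors are distorted too.** That may happen, but the calculations here cover only an endoscopist-level factor.

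A fair warning about the remedy also stands. At 10%, an arm has about 0.10 × 315 = 31.5 to 0.10 × 394 = 39.4 events. A model with both endoscopist and patient levels may then be hard to fit.

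**Conclusion.** The concern holds in conditional form. The plan makes no allowance for lesions sharing an endoscopist. If an endoscopist characteristic is tested by logistic regression on lesions as section 7 reads, its type I error exceeds 5% whenever results vary between endoscopists. The size is about 7–27% per arm at 394 lesions and somewhat lower at about 315. It rests on assumed values: 10 to 24 endoscopists of equal workload, 10% events, SD 0.4 to 0.8, and a two-level factor. If endoscopists do not differ, the error is about 5% and there is no problem.

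A reader might infer that the main result is at risk. This point does not touch the primary comparison or the sample size. It concerns two secondary objectives and should be corrected before analysis because the correction is cheap.

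**What to change.** In section 7, for the two factor objectives:

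1. List the candidate factors, marking which are endoscopist-level, and state the number of endoscopists.
2. Fit logistic regression with a random intercept for endoscopist (melogit in Stata 13). Add a patient level, or patient-level robust variance, only if the data support it.
3. Test endoscopist characteristics against a t distribution with degrees of freedom equal to the number of endoscopists minus the number of endoscopist-level parameters, counting the intercept. With 14 endoscopists and one two-level characteristic this is 14 − 2 = 12.
4. State in advance the number of endoscopists below which these characteristics will only be described.
5. Do not use fixed endoscopist effects here. They absorb every endoscopist-level factor, which then cannot be estimated.

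The cost is a few sentences and a few lines of code, with no extra patients or data. The price is wider intervals for endoscopist-level factors and a slightly conservative test if endoscopists do not in fact differ.
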